8.6.2 Analysis of Secondary Efficacy Variables

For secondary efficacy endpoints, each comparison between treatment groups will be conducted at $\alpha=0.05$ (two-sided). Secondary study endpoints will be analyzed only at the final analysis to determine the statistical significance, if any, between the treatment groups. Study-wise Type I error will be controlled using a sequential hierarchical approach, as shown in the figure below. That is, if the primary comparison is statistically significant, the secondary endpoints will be analyzed as secondary endpoints in order of the list below and will continue as long as the obtained 2-sided probability is equal to or less than 0.05. If a probability of greater than 0.05 is obtained, the inferential analysis of secondary endpoints will stop and not proceed further down the ordered list. In this manner the overall study alpha is protected and no further adjustment for multiplicity of analyses is required. If a probability of greater than 0.05 is obtained for an endpoint then the analysis of that endpoint and the endpoints further down the ordered list will still be presented but will be considered as exploratory endpoints rather than secondary endpoints.

Hierarchical approach to control study-wise Type I error of primary and secondary efficacy endpoints

^a Type I error is controlled at $\alpha=0.05$ (two-sided) over the 2 planned interim analyses and final analysis.

8.6.2.1 Time to Progression (TTP) according to RECIST v1.1 criteria by investigator determination

TTP rates will be derived from the Kaplan-Meier estimates for each treatment group; 3, 6, 9, and 12-month TTP rates will be presented, together with 95% CIs. Quartiles will be presented and 95% CIs will be calculated on the quartiles for each treatment group. A log-rank (two-sided) test will be used to compare TTP between the two treatment groups at a 0.05 significance level. The HR and corresponding 95% CI will be computed from a Cox proportional hazards model. Plots of the Kaplan-Meier curves will be provided for each treatment group. This analysis will be performed on both the mITT and PP populations.

$$\text{TTP (Months)} = (\text{Date of event/censor} - \text{Date of Randomization} + 1) / 30.4375.$$

The censoring is performed in the following order:

- 1) If a patient does not have a baseline tumor assessment, then the TTP time will be censored at the randomization date, regardless of whether or not radiological disease progression (i.e. PD) has been observed.
- 2) If a patient received a subsequent HCC therapy before PD or in the absence of PD, the TTP time will be censored at the last valid (i.e. evaluable) post baseline radiological tumor assessment on or before the start date of the subsequent HCC therapy. If the patient has no valid post-baseline radiological tumor assessments on or before the start date of the subsequent HCC therapy, the patient will be censored at the randomization date.
- 3) If a patient is known not to have PD and did not receive subsequent HCC therapy, the TTP time will be censored at the date of death* or last valid post baseline radiological tumor assessment date in the absence of death, or at the randomization date if the patient does not have any valid post-baseline radiological tumor assessments or death.
- 4) If a patient had PD immediately after two or more missed visits (Note: a response of NE at a visit is not considered as a missed visit), the patient will be censored at the time of the last valid post baseline radiological tumor assessment date that occurred before the missed visits. If the patient has no valid post-baseline radiological tumor assessments before the missed visits, the patient will be censored at the randomization date.
 - For example, if a patient had a tumor assessment at Week 8, but did not have tumor assessments at Weeks 16 and 24, and then had PD at the Week 32 assessment (i.e. after 2 missed visits), then the TTP time would be censored at the date of the Week 8 assessment.
 - Given the scheduled visit scheme of tumor assessments (i.e. every 8 weeks), the definition of 2 missed visits will equate to 16 weeks since the previous tumor assessment, or since the randomization date if no previous post-baseline tumor assessment.

* Note: Censoring at the date of death, in the above censoring rules, is according to US Food and Drug Administration (FDA) guidance⁸. However, a sensitivity analysis of TTP, excluding censoring at the date of death (i.e. censoring at the last valid post baseline radiological tumor assessment date instead) with all other censoring rules described above still used, will also be performed.

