9.0 STUDY VISITS, EVALUATIONS AND PROCEDURES

9.1 STUDY VISITS

Study treatment visits should occur at the time intervals outlined below and in the study visit schedule in Section 3.0. All study visits that take place after the screening/randomization period should occur within +/- 14 days of the designated time interval for that study visit.

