9.2.16 EFFICACY IMAGING – CT/MRI

Baseline efficacy imaging scans will be obtained during screening. Efficacy assessment scans will be taken in accordance with SOC clinical management guidelines every 8 weeks post randomization until death. Most patients will be evaluated by CT images. MRI images are also permitted. The imaging modality used at baseline must continue to be used for all efficacy images throughout the study. Duplicate DICOM images will be submitted to the sponsor or designee to permit future Central Imaging Review in accordance with image submission instructions.

Triple Phase Spiral CT abdomen – must be performed with cuts of 10 mm or less in slice thickness contiguously in the axial plane. From these images, hepatic and extra-hepatic lesions will be read according to the RECIST criteria v1.1 (Appendix 3).

Spiral CT chest and pelvis – must be performed with cuts of 10 mm or less in slice thickness contiguously in the axial plane. From these images, extra-hepatic lesions will be read according to the RECIST criteria v 1.1 (Appendix 3).

For Secondary Study Endpoints based on radiographic assessment, the investigator will identify, read and measure hepatic lesions for size at Baseline using RECIST v 1.1 criteria. At all subsequent follow-up visits, the images (using the same modality) will be read and measured and compared back to the Baseline images and then categorized as Complete Response, Partial Response, Stable, or Progressing at each time point using RECIST v 1.1 (Appendix 3). These data will be captured on the eCRF and may be summarized showing tumor response over time.

The tumor response, according to the mRECIST criteria and based on a blinded centralized independent imaging assessment, will be recorded as an exploratory endpoint. Investigators will not be required to perform mRECIST assessments.

[REDACTED]

[REDACTED]

[REDACTED]

[REDACTED]

[REDACTED]

[REDACTED]

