6.4.2.4 Time to Untreatable Progression

This secondary endpoint, time to untreatable progression, is defined as the time from date of randomization to date of untreatable progression, where untreatable progression is defined as one of the following events:

- Intolerance to sorafenib
- Occurrence of specific contraindications to sorafenib
- Assessment of progression in the target lesions, occurrence of new lesions after treatment, or death due to progression and, for patients randomized to the treatment group, a maximum of 2 re-treatments with TheraSphere
- Occurrence of specific contraindications to TheraSphere and or appearance of lung/intestinal shunts or anatomical constraints not correctable by radiological procedures for the Treatment group
- Confirmed extra-hepatic metastases
- Deterioration of liver function (Child Pugh score $>B7$)
- Clinical progression to ECOG performance status >1 . Such deterioration in performance status should be observed at two subsequent evaluations at 8 week intervals.

The investigator will determine whether the patient met any of the protocol specified conditions. A response of yes to the question of “Is this progression considered untreatable according to the protocol definition?” on the Determination of Response or Progression CRF page will be used to indicate untreatable progression.

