8.3.3 Per Protocol (PP) Population

The Per Protocol population is the subset of the mITT population excluding patients with major protocol deviations which may affect the efficacy evaluation. Patients in the PP population will be analyzed according to the treatment group to which they were randomized.

Major protocol deviations resulting in a patient being excluded from the PP population will include, but may not be limited to, the following:

- Baseline imaging assessment not performed
- Baseline imaging assessment performed >42 days prior to date of randomization (note that although the screening period for baseline imaging assessment was 28 days, an additional 14-day window is being applied so that only baseline imaging assessments >42 days before randomization will be deemed to be a major protocol deviation that may affect the efficacy evaluation)
- Post-randomization imaging assessments not performed for 3 consecutively planned timepoints (i.e. the number of days between imaging assessments is >224 days), defined as
 - the first post-randomization imaging assessment, prior to progression (i.e. prior to date of progression) as assessed by investigator according to RECIST 1.1, occurs at >32 weeks (i.e. >224 days) after randomization, or
 - any post-randomization imaging assessment, prior to progression as assessed by investigator according to RECIST 1.1, occurs at >32 weeks (i.e. >224 days) after the previous post-randomization imaging assessment
- Randomized study treatment not received (TheraSphere and/or sorafenib) prior to progression as assessed by investigator according to RECIST 1.1
- Y90 (including TheraSphere) received by patients in the control arm prior to progression assessed by investigator according to RECIST 1.1
- TheraSphere dose absorbed by perfused volume (as defined in Section 6.5.1.1) lower than the protocol stated range of 120 Gy – 10% (i.e. <108 Gy) prior to progression as assessed by investigator according to RECIST 1.1
- Bilobar disease at baseline (as defined in Section 6.5.1.1) but only one lobe treated with TheraSphere prior to progression assessed by investigator according to RECIST 1.1
- For patients enrolled under all protocol versions implemented:
 - For the control arm:
 - Start of sorafenib >28 days after randomization

- o For the treatment arm:
 - First administration of TheraSphere prior to progression >35 days after randomization, or

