 - Given the scheduled visit scheme of tumor assessments (i.e. every 8 weeks), the definition of 2 missed visits will equate to 16 weeks since the previous tumor assessment, or since the randomization date if no previous post-baseline tumor assessment.

A sensitivity analysis of TTUP, excluding censoring at the date of death for any reason other than progression of disease (i.e. censoring at the last valid post baseline radiological tumor assessment date instead) with all other censoring rules described above still used, will also be performed.

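### The missed-visit censoring rule equates two missed visits with 16 weeks, which on an 8-week schedule is the gap to an event found after only one

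*SAP*

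**What the plan says.** Protocol 9.2.16 schedules efficacy scans "every 8 weeks post randomization until death". Protocol 9.1 adds that visits "should occur within +/- 14 days of the designated time interval for that study visit".

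Censoring rule 4 for TTP (SAP 8.6.2.1) begins "If a patient had PD immediately after two or more missed visits" and moves the patient's time back to the last valid scan before the gap, or to randomization if there is none. Its example is a patient scanned at Week 8 who "did not have tumor assessments at Weeks 16 and 24, and then had PD at the Week 32 assessment (i.e. after 2 missed visits"; that patient is censored at Week 8. The next bullet gives the time equivalent: "the definition of 2 missed visits will equate to 16 weeks since the previous tumor assessment", or since randomization if there is no earlier post-baseline scan. It has no inequality sign.

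The same 16-week bullet appears for TTUP (8.6.2.2), TTSP (8.6.2.3), TTDQoL (8.6.3.2), PFS and the duration endpoints (both 8.6.6). Only TTP has an example. SAP 6.2.2 states that the analysis visit windows are not used for time-to-event endpoints.

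The Per Protocol definition (SAP 8.3.3) makes a similar conversion: "Post-randomization imaging assessments not performed for 3 consecutively planned timepoints (i.e. the number of days between imaging assessments is >224 days".

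**The concern.** The rule in words and the rule in weeks disagree. An event found at a visit 16 weeks after the last assessment follows one missed visit, yet the bullet gives that gap as the definition of two. With the analysis windows excluded, 16 weeks is the only stated time criterion, so a programmer could reasonably code it.

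Applied literally, valid events after a single missed visit become censored observations dated at the previous assessment, or at randomization. Two programmers could also produce different event counts from the same text. The planned TTP and TTUP sensitivity analyses change only the handling of deaths, "with all other censoring rules described above still used", so no planned analysis would show the effect.

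OS does not use the rule. Under SAP 8.6.2 a secondary endpoint is confirmatory only if OS and every earlier endpoint in the ordered list are significant. PFS and the duration endpoints are additional analyses. Both arms share the 8-week schedule and nothing in the documents suggests unequal missed visits, so no bias between arms is claimed.

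**Working it through.** **Inputs.** Interval 8 weeks = 56 days (Protocol 9.2.16); window ±14 days (Protocol 9.1); stated equivalent 16 weeks = 112 days (SAP 8.6.2.1).

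**The plan's figure.** 2 × 8 = 16 weeks is the scheduled date of the second missed visit. It is not the date at which a later visit can find an event.

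**Gap to a visit-detected event.** After k missed visits the gap is (k + 1) × 56 days. The window adds ±28 days between two visits, or ±14 days from randomization.

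| Missed | Nominal gap | Range between visits | Range from randomization |
|---|---|---|---|
| 1 | 112 d (16 wk) | 84–140 | 98–126 |
| 2 | 168 d (24 wk) | 140–196 | 154–182 |
| 3 | 224 d (32 wk) | 196–252 | 210–238 |

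The SAP example (32 − 8 = 24 weeks) is the second row. The 224 days in the Per Protocol rule is the nominal gap in the third. The 16 weeks belongs to the first.

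**Share of single-miss events beyond 112 days, exact.** Give each of the two visits an offset of −14 to +14 days, all equally likely (an assumption): 29 × 29 = 841 pairs, of which 29 give exactly 112 days.

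- Gap >112: (841 − 29)/2 = 406, and 406/841 = 48.3%.
- Gap >=112: 435/841 = 51.7%.

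A longer gap is more likely to contain the progression, so weight by gap length. The mean gap is 112, and the positive differences d add the sum of d(29 − d) for d = 1 to 28, which is 4,060.

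- Gap >112: (112 × 406 + 4,060)/(841 × 112) = 49,532/94,192 = 52.6%.
- Gap >=112: (49,532 + 29 × 112)/94,192 = 52,780/94,192 = 56.0%.

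**Simulation of progression.** 500,000 patients per scenario; exponential TTP with an assumed median of 5.5 months (the central-review figure for sorafenib in Protocol 5.3); independent misses at 5%, 10% or 20%; deaths and subsequent-therapy censoring ignored. Share of progressions after exactly one missed visit that a 112-day cut censors:

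| Visit scatter | >112 | >=112 |
|---|---|---|
| On schedule | 0% | 100% |
| Uniform ±3 d | 43–44% | 58% |
| Uniform ±7 d | 49% | 55% |
| Uniform ±14 d | 52% | 55–56% |
| Normal, SD 10 d | 53% | 56% |

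The shares barely change with the miss rate. For illustration, at ±14 days the wrongly censored events per 100 progressions (> / >=) are 4.2 / 4.5 at 5% missed, 7.7 / 8.3 at 10% and 12.6 / 13.5 at 20%.

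**Alternative cuts.** A >140-day cut censors no single-miss progression when visits are in window (2.1–2.2% with SD 10) and leaves uncensored under 0.1% of those after two or more misses (1.2–1.5% with SD 10). A >168-day cut, the Per Protocol convention carried to two visits, leaves 48–57% of two-miss progressions uncensored with spreads of ±3 to ±14 days, and all of them on schedule.

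**Deaths.** A death need not wait for a visit. If the last assessment was u days off schedule, the second missed visit's window closes 112 + 14 − u = 126 − u days later, that is 112 to 140 days. Sixteen weeks is therefore nominally right here. With exponential OS (median 10.7 months, Protocol 10.1), the same miss rates and spreads of 0, ±7 and ±14 days, 31–36% of deaths after exactly two missed visits fall at or before 140 days (32–39% in a repeat run). A >112-day cut misses none of these and wrongly censors 2–14% of deaths after exactly one (1–14% in the repeat). One cut cannot serve both kinds of event.

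**TTSP.** Rule 4 there works on ECOG assessments, but its bullet counts from the previous tumor assessment. Table 7 (SAP 6.4.2.5) counts as events two patterns with one missing visit, a 16-week ECOG gap, which a >=16-week reading would censor.

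**The case against.** The strongest reply is that the operative rule is the visit count, and the bullet only says that sixteen weeks without an assessment spans two scheduled visits. A patient scanned at 16 weeks did not miss that visit. On this view the > reading is implied, Table 7 and the example exclude >=, and on-schedule visits lose nothing.

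Part of this stands. The intent is recoverable for TTP, and >= is hard to square with Table 7. But > is harmless only if every visit falls exactly on schedule. With scatter of ±3 days it already censors 43–44% of single-miss progressions. The example does not restrain the bullet either, because a 168-day gap is censored under any of these readings.

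A second point also stands in part. The Per Protocol rule says >224 days, and carried to two visits (>168) it would not censor the SAP's own 168-day example. It supports the way visits are counted, not the choice of cut. It is also fair that the impact is unknown, that the per-100 figures rest on assumed miss rates, and that a single visit-count rule could serve all event types. None of this makes 16 weeks correct for a visit-detected event.

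**Conclusion.** The concern holds. For events found at a visit, the 16-week bullet contradicts the rule it is meant to implement, and it does so in six places. Read as a 112-day cut, it would censor about half of the progressions after exactly one missed visit under realistic scatter: 52% (>) or 55–56% (>=) at uniform ±14 days. On perfectly timed visits it would censor none or all of them, according to the operator. These shares assume independent misses and symmetric scatter. How many patients are affected cannot be found, because the documents give no missed-visit rate. The cost is lost and backdated events and ambiguous programming in the secondary and additional endpoints. OS is untouched. This should be fixed, but it does not threaten the primary analysis.

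**What to change.** 1. For visit-detected events (progression, untreatable progression found at a scan, ECOG >1, FACT-Hep decline), replace 16 weeks in each bullet with a threshold and operator that match two missed visits, for example >140 days (20 weeks) since the previous assessment of the relevant type, or since randomization. PFS needs only this, since its rule 4 names progression alone.
2. For deaths that count as events in TTDQoL and the duration endpoints, censor only if two scheduled visits had passed without an assessment. Take each visit as a multiple of 56 days from randomization ±14 days (SAP 6.1, Table 2, footnote 8). Write this into the bullet, because SAP 6.2.2 rules out the analysis windows. Using the visit count for all events would also be acceptable.
3. Apply the visit count to TTUP events not dated at a visit. SAP 6.4.2.4 includes "occurrence of new lesions after treatment, or death due to progression"; state how such deaths are dated, since the event is identified from a case report form page.
4. For TTSP, count from the previous ECOG assessment and say that Table 7 governs.
5. If programming is complete, confirm and document the threshold that was coded.

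A sensitivity analysis that counts events regardless of missed visits is optional. The cost is wording in six places, one constant with its operator, and a short visit-count derivation. No new data are needed.

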8.6.2.2 Time to Untreatable Progression (TTUP)

TTUP rates will be derived from the Kaplan-Meier estimates for each treatment group; 3, 6, 9, and 12 month TTUP rates will be presented, together with 95% CIs. Quartiles will

be presented and 95% CIs interval will be calculated on the quartiles for each treatment group. A log-rank (two-sided) test will be used to compare TTUP between the two treatment groups at a 0.05 significance level. The HR and corresponding 95% CI will be computed from a Cox proportional hazards model. Plots of the Kaplan-Meier curves will be provided for each treatment group. This analysis will be performed on both the mITT and PP populations.

TTUP (Months) = (Date of event/censor – Date of Randomization +1)/ 30.4375.

The censoring is performed in the following order:

- 1) If a patient does not have a baseline tumor assessment, then the TTUP time will be censored at the randomization date, regardless of whether or not untreatable PD has been observed.
- 2) If a patient received a subsequent HCC therapy before untreatable PD or in the absence of untreatable PD, the TTUP time will be censored at the last valid (i.e. evaluable) post baseline radiological tumor assessment on or before the start date of the subsequent HCC therapy. If the patient has no valid post-baseline radiological tumor assessments on or before the start date of the subsequent HCC therapy, the patient will be censored at the randomization date.
- 3) If a patient is known not to have untreatable PD and did not receive subsequent HCC therapy, the TTUP time will be censored at the date of death or last valid post baseline radiological tumor assessment date in the absence of death, or at the randomization date if the patient does not have any valid post-baseline radiological tumor assessments or death.
- 4) If a patient had untreatable PD immediately after two or more missed visits (Note: a response of NE for a visit is not considered as a missed visit), the patient will be censored at the time of the last valid post baseline radiological tumor assessment date that occurred before the missed visits. If the patient has no valid post-baseline radiological tumor assessments before the missed visits, the patient will be censored at the randomization date.
 - Given the scheduled visit scheme of tumor assessments (i.e. every 8 weeks), the definition of 2 missed visits will equate to 16 weeks since the previous tumor assessment, or since the randomization date if no previous post-baseline tumor assessment.

A sensitivity analysis of TTUP, excluding censoring at the date of death for any reason other than progression of disease (i.e. censoring at the last valid post baseline radiological tumor assessment date instead) with all other censoring rules described above still used, will also be performed.

8.6.2.3 Time to Symptomatic Progression (TTSP)

TTSP rates will be derived from the Kaplan-Meier estimates for each treatment group; 3, 6, 9, and 12 month TTSP rates will be presented, together with 95% CIs. Quartiles will be presented and 95% CIs will be calculated on the quartiles for each treatment group. A log-rank (two-sided) test will be used to compare TTSP between the two treatment groups at a 0.05 significance level. The HR and corresponding 95% CI will be computed from a Cox proportional hazards model. Plots of the Kaplan-Meier curves will be provided for each treatment group. This analysis will be performed on both the mITT and PP populations.

TTSP (Months) = (Date of first ECOG >1/censor – Date of Randomization + 1)/ 30.4375.

The censoring is performed as follows:

- 1) If a patient does not have a post baseline ECOG assessment, then the TTSP will be censored at the randomization date, regardless of whether or not symptomatic progression has been observed.
- 2) If a patient received a subsequent HCC therapy before symptomatic progression or in the absence of symptomatic progression (note that for this scenario a subsequent HCC therapy may occur before the assessment of ECOG>1 or before either confirmation of ECOG>1 at the first two subsequent assessments at least 8 and 16 weeks later, respectively), the TTSP time will be censored at the last valid post baseline ECOG assessment on or before the start date of the subsequent HCC therapy. If the patient has no post-baseline ECOG assessments on or before the start date of the subsequent HCC therapy, the patient will be censored at the randomization date.
- 3) If a patient did not have a symptomatic progression and did not receive subsequent HCC therapy, the TTSP time will be censored at the last post baseline ECOG assessment date or at the randomization date if the patient does not have any post-baseline ECOG assessments.
- 4) If a patient had symptomatic progression immediately after two or more missed visits (note that for this scenario two or more missed visits may occur before the assessment of ECOG>1 or before either confirmation of ECOG>1 at the first two subsequent assessments at least 8 and 16 weeks later), the patient will be censored at the last post baseline ECOG assessment before the missed visits. If the patient has no post-baseline ECOG assessments before the missed visits, the patient will be censored at the randomization date.
 - Given the scheduled visit scheme of tumor assessments (i.e. every 8 weeks), the definition of 2 missed visits will equate to 16 weeks since the previous tumor assessment, or since the randomization date if no previous post-baseline tumor assessment.

8.6.2.4 Objective Response Rate (ORR) according to RECIST v1.1 criteria by investigator determination

ORR will be computed for the two treatment groups as proportion of CR+PR over the total number of patients in the specified population. The 95% CIs for the ORR for each of the treatment groups will be computed according to Wilson (1927).

ORR, as determined by the investigator using RECIST 1.1, will be compared between treatment groups using the continuity adjusted Wald test, and the corresponding 95% CI for the difference in ORRs between the two treatment groups will be calculated. This analysis will be performed for each time point and the best overall response on both the mITT and PP populations.

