6.4.2.5 Time to Symptomatic Progression

Time to symptomatic progression (TTSP) is defined as the time from date of randomization to date of assessment of ECOG performance status >1 with or without tumor progression based on investigator assessment according to RECIST criteria v1.1. The symptomatic progression is confirmed at the first two subsequent evaluations at least 8 and 16 weeks later, respectively. The date of the first ECOG performance status >1 will be used as the event date in the TTSP analysis (assuming ECOG performance status >1 at the first two subsequent evaluations at least 8 and 16 weeks later, respectively). Illustrative examples are provided in Table 7.

Table 7 Examples of Symptomatic Progression

Week X	Week X+8	Week X+16	Week X+24	Week X+32	TTSP Event
ECOG>1	ECOG>1	ECOG>1	ECOG≤1	ECOG≤1	Yes, event at Week X

ECOG>1	ECOG>1	Missing	ECOG>1	ECOG≤1	Yes, event at Week X
ECOG>1	Missing	ECOG>1	ECOG>1	Missing	Yes, event at Week X
ECOG>1	ECOG≤1	ECOG>1	ECOG>1	Missing	No
ECOG>1	No further ECOG assessments				No
ECOG>1	ECOG>1	No further ECOG assessments			No

Week X denotes that week of the first occurrence of ECOG >1

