- If a patient had a deterioration in QoL immediately after two or more visits where total FACT-hep score could not be evaluated (e.g. missed visits or visits missing items to derive total FACT-hep score), the patient will be censored at the last post baseline FACT-hep assessment before the missed visits where total FACT-hep score could be evaluated. If the patient has no post baseline total FACT-hep scores before the missed visits, the patient will be censored at the randomization date.
 - Given the scheduled visit scheme of FACT-hep assessments (i.e. every 8 weeks), the definition of 2 missed visits will equate to 16 weeks since the previous FACT-hep assessment where total FACT-hep score could be evaluated, or since the randomization date if no previous post-baseline total FACT-hep scores.

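### The TTSP missed-visit rule counts time from the last tumor scan, not the last ECOG assessment, so a confirmed ECOG decline can be censored when scans lapse

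*SAP*

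**What the plan says.** SAP 6.4.2.5 defines the TTSP event by the "date of assessment of ECOG performance status >1 with or without tumor progression based on investigator assessment". Two confirmations are needed: "The symptomatic progression is confirmed at the first two subsequent evaluations at least 8 and 16 weeks later, respectively". Table 7 in that section gives worked patterns, stated in ECOG values only.

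SAP 8.6.2.3, rule 4, censors a symptomatic progression that comes straight after two or more missed visits. It can act at three points, since "two or more missed visits may occur before the assessment of ECOG>1 or before either confirmation of ECOG>1". When it acts, "the patient will be censored at the last post baseline ECOG assessment before the missed visits".

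The bullet under rule 4 then defines the gap: "the definition of 2 missed visits will equate to 16 weeks since the previous tumor assessment". For a patient never scanned after baseline, the clock starts at randomization instead.

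The parallel bullet for TTDQoL in SAP 8.6.3.2 is tied to its own instrument: "the definition of 2 missed visits will equate to 16 weeks since the previous FACT-hep assessment where total FACT-hep score could be evaluated".

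**The concern.** The event, its confirmations and the censoring date are all read from ECOG, but the trigger for censoring is read from CT/MRI. The trigger wording is the same as in SAP 8.6.2.2 for TTUP, and the SAP gives no reason for applying it to an ECOG endpoint. A missed-visit rule is meant to remove events whose timing is uncertain because the endpoint was not being measured. Here it can remove events whose timing is fully documented, and keep events that follow a real gap in ECOG.

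TTSP is a listed secondary endpoint, compared by a two-sided log-rank test at 0.05 within the hierarchy of SAP 8.6.2. A programmer would have to code a rule that disagrees with its own censoring date, or depart from the text without documentation, in an open-label trial.

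**Working it through.** **Inputs.** ECOG and CT/MRI belong to the same 8-weekly follow-up visit (Protocol synopsis, Study Visits and Follow-up), with a window of ±14 days (Protocol 3.0, footnote 8). Confirmations fall at least 8 and 16 weeks after onset (SAP 6.4.2.5). The gap is 16 weeks (SAP 8.6.2.3).

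**The plan's figure.** 2 missed visits × 8 weeks = 16 weeks. This reproduces as a count of visits. As a gap between attended visits, two missed visits span 3 × 8 = 24 weeks, as in the SAP's own TTP example in 8.6.2.1 (Week 8 to Week 32: 32 − 8 = 24). The per-protocol rule in SAP 8.3.3 uses the same convention: three missed timepoints correspond to (3 + 1) × 8 = 32 weeks = 224 days.

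**Literal rule on explicit patterns.** The SAP does not say whether the threshold is at least 16 or more than 16 weeks, so both were tried.

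| Pattern | Scan clock (as written) | ECOG clock |
|---|---|---|
| Scans and ECOG all attended; ECOG >1 at Weeks 16, 24, 32 | Event at Week 16 | Event at Week 16 |
| Last scan Week 8; ECOG complete, >1 at Weeks 16, 24, 32 | Censored under both readings (gap 16 weeks at Week 24, 24 at Week 32) | Event at Week 16 |
| No post-baseline scan; ECOG >1 at Weeks 8, 16, 24 | Censored under both readings (gap 16 weeks at Week 16, 24 at Week 24) | Event at Week 8 |
| Last scan at onset, Week 16; ECOG >1 at Weeks 16, 24, 32 | Censored if at least 16 (gap 32 − 16 = 16); event if more than 16 | Event at Week 16 |
| All scans done; ECOG missed at Weeks 16 and 24, then >1 at Weeks 32, 40, 48 | Event kept | Censored (gap 32 − 8 = 24) |

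The third row is general. With no post-baseline scan the clock starts at randomization. Onset is later than randomization, and the second confirmation is at least 16 weeks after onset, so it is always more than 16 weeks from randomization. Such a patient cannot be a TTSP event, however complete the ECOG record.

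**Is changing the instrument enough?** Table 7 rows 2 and 3 each contain one missed ECOG visit and are shown as events at Week X. The gaps are (X + 24) − (X + 8) = 16 weeks and (X + 16) − X = 16 weeks. An ECOG clock read as at least 16 weeks would censor both. Read as more than 16 weeks it keeps them at nominal dates, but a visit a few days late would tip them over. With ±14 days at each end, one missed visit gives 112 ± 28 = 84 to 140 days and two give 168 ± 28 = 140 to 196 days. The dividing line is therefore 140 days (20 weeks), not 112.

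**Size.** The documents give no rate of lapsed scans. For illustration only, assume complete ECOG, onset at visits 1 to 6, 0–20% of scans missed at random, and scans stopping at onset in 0–50% of patients. The share of confirmed events censored is 0% with no lapse. At the 20%/50% corner it is 11–15% if the rule means more than 16 weeks and 55–73% if it means at least 16; the range within each reading depends on whether a same-day scan resets the clock. These are conditional figures, not estimates for this trial.

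**The case against.** The strongest reply is that the plan does not schedule ECOG and scans apart. They share the 8-weekly visit, and Protocol 9.2.16 plans scans until death, not until progression. Patients who stop treatment for progression and cannot attend are followed by telephone (Protocol 9.1.2.2 and 9.1.3.5), so for them both assessments may lapse together. Rule 2 of SAP 8.6.2.3 already censors patients who start subsequent HCC therapy before onset or before either confirmation, which removes some patients whose scans stopped after progression. Table 7 row 1 counts three consecutive ECOG >1 values as an event with no scan condition, and a visit with an ECOG on record is hard to call missed. A sensible programmer might therefore read the bullet as ECOG.

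Much of this stands. It confines the fault to patients whose scans lapse while ECOG continues, and it rules out any firm figure. It does not rescue the wording. A missed-visit rule exists for departures from schedule, and the SAP expects imaging gaps: 8.3.3 excludes patients with gaps over 224 days from the per-protocol population, while the mITT analysis keeps them. The conflict with Table 7 shows that the bullet needs correction.

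A reader might infer that every patient whose last scan is at or before onset is censored. That fails for a scan exactly at onset with visits on schedule if the threshold means more than 16 weeks.

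**Conclusion.** The TTSP missed-visit definition is wrong as written and should be fixed. Followed literally, it censors confirmed symptomatic progressions with complete ECOG data when scans lapse, always so when there is no post-baseline scan, and it overlooks real ECOG gaps when scans were done. If both assessments are done as scheduled, the effect is nil.

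Two stronger conclusions are tempting. One is that a large share of TTSP events will be lost; that needs a scan-stopping rate the documents do not supply, and an allowance for rule 2 censoring. The other is that the TTSP log-rank test and hazard ratio are biased between arms. This is possible if scans lapse differently by arm, but nothing in the documents shows that they do, or in which direction. Overall survival does not use this rule and is unaffected.

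**What to change.** In the bullet under rule 4 of SAP 8.6.2.3, replace tumor assessment with ECOG assessment throughout, including the visit-schedule clause and the randomization fallback, as 8.6.3.2 does for FACT-Hep.

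In the same edit, state the threshold and its inequality so that one missed ECOG visit (nominal 16-week gap, Table 7 rows 2 and 3) remains an event and two missed visits (nominal 24-week gap) trigger censoring, with allowance for the ±14-day window. A gap of more than 140 days does this, apart from the extreme two-visit gap of exactly 140 days; counting missed scheduled ECOG visits directly would also serve. Run the coded rule against every row of Table 7 before use.

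The cost is one SAP bullet and one derivation line, best settled before database lock. If TTSP has already been programmed on the scan clock, rerun it on the ECOG clock and report how many patients change status in each arm.
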